3.2 Schedule of Assessments

For the complete schedule of assessments, refer to Section 6 (Schedule of Events) in the clinical study protocol.

3.3 Treatments

3.3.1 Treatments Administered

3.3.1.1 Nanatinostat (VRx-3996)

Nanatinostat (VRx-3996) is a hydroxamic acid-based histone deacetylase inhibitor and is available as 10-mg tablets.

All patients will receive nanatinostat orally once or twice daily (at breakfast or at breakfast and lunch, respectively) on Days 1 to 4 per week (i.e., 4 days on, 3 days off),

or Days 1 to 7 per week. Following the completion of the 28-day Cycle 1, patients will continue dosing in 21-day cycles until discontinuation.

3.3.1.2 Valganciclovir

Valganciclovir is a cytomegalovirus nucleoside analogue DNA polymerase inhibitor and is available as 450-mg tablets packaged in bottles.

The daily oral dose of valganciclovir is 900 mg once daily; 900 mg twice daily for 21 days (at breakfast and dinner) followed by a subsequent dose reduction to 900 mg once daily; or 450 mg twice daily at breakfast and lunch, in combination with nanatinostat. Following the completion of the 28-day Cycle 1, patients will continue to receive the combination of nanatinostat and valganciclovir in 21-day cycles until discontinuation.

Valganciclovir doses should be adjusted for patients who develop an elevated creatinine level while on study.

3.3.1.3 Pembrolizumab

Pembrolizumab is a humanized monoclonal PD-1 inhibitor antibody (IgG4/kappa isotype with a stabilizing sequence alteration in the Fc region) produced in Chinese hamster ovary cells by recombinant DNA technology. Pembrolizumab is available for injection in 100 mg/4 mL (25 mg/mL) in a single-dose vial.

The starting provisional dose of pembrolizumab is 200 mg IV every 3 weeks.

3.3.1.4 Sequence of Study Drug Administration

Patients will be administered study drugs on a treatment schedule determined by study phase and dose level. For a detailed description of different dosing administration schedules for each dose level, refer to Section 5.3.3 (Sequence of Study Drug Administration) of the clinical study protocol.

3.3.2 Method of Assigning Patients to Treatment Groups

Patients with EBV^+ RM-NPC will be enrolled in groups of 3 to 6 in the Phase 1b escalating nanatinostat dose cohorts to determine the RP2D of nanatinostat in combination with valganciclovir. Patients in screening when the last patient is enrolled in a cohort may also be enrolled if eligible.

For Phase 2, following determination of the RP2D, approximately 40 patients will be randomized into one of two dose optimization cohorts receiving nanatinostat at the RP2D or at the ' $<RP2D$ ' and valganciclovir twice daily.

Following confirmation of the RP2D, patients with EBV^+ RM-NPC will be randomly assigned 1:1 using a centralized interactive randomization system to either nanatinostat and valganciclovir treatment or nanatinostat and valganciclovir in combination with pembrolizumab treatment in the Phase 2 dose expansion period. Randomization will be stratified by prior anti-PD-L1 treatment exposure. Pembrolizumab will be administered at 200 mg IV every 3 weeks for those patients randomly assigned to the nanatinostat, valganciclovir, and pembrolizumab arm. An early safety analysis after the first 6

patients are randomized to this treatment arm and followed for at least 2 cycles (7 weeks) of treatment will be performed.

In addition, up to 10 patients with EBV^+ non-NPC solid tumors will be enrolled into an exploratory proof-of-concept cohort. The dose and regimen will be based on data collected and analyzed from prior cohorts after an RP2D is determined in consultation with the SMC to predict the appropriate recommended dose for the non-NPC solid tumor population prior to commencing enrollment.

3.3.3 *Blinding Procedures*

This is an open-label study so treatment assignments will not be blinded.

3.4 Efficacy and Safety Variables

3.4.1 *Efficacy Variables*

3.4.1.1 *Primary Efficacy Variable*

Tumor responses will be assessed by the Investigator per RECIST v1.1 using MRI or CT scan assessments. For patients receiving pembrolizumab, tumor responses will also be assessed per immunologic RECIST (iRECIST). Tumor imaging will be repeated to confirm disease progression using iRECIST.

The primary efficacy endpoint is ORR, defined as the percentage of patients with a CR or PR as assessed by RECIST v1.1 within the first 26 weeks (6 months) of treatment. The ORR will also be calculated using iRECIST for patients receiving pembrolizumab.

3.4.1.2 *Secondary Efficacy Variables*

Secondary efficacy endpoints include the following:

- Time to response (TTR) – defined as the interval from the start of study drug treatment to the date of first documented CR or PR per RECIST or iRECIST.
- Duration of response (DOR) – defined as the interval of time from the date of first observed CR or PR to the date of documented disease progression or death due to any cause, whichever occurs first. Dates of progression and censoring will be determined as described in [Section 4.5.5.2](#);
- Disease control rate (DCR) – defined as the percentage of patients having a CR, PR, or stable disease (SD) at any time during treatment;
- Progression-free survival (PFS) – defined as the interval of time from the start of study drug treatment to the date of first documented disease progression, initiation of new antineoplastic therapy, withdrawal of consent, loss to follow-up, or death due to any cause, whichever occurs first. Dates of progression and censoring will be determined as described in [Section 4.5.5.2](#); and
- Overall survival (OS) – defined as the interval of time from the start of study drug treatment to the date of death due to any cause. Patients without

documentation of death at the time of analysis will be censored at the date the patient was last known to be alive.

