7.3.3. Discontinuation of Study Treatment

Patients will continue study treatment until disease progression, unacceptable toxicity, start of new anti-neoplastic therapy, withdrawal of consent by the patient, patient is lost to follow-up, or discontinuation from the study due to any other reason (eg, Sponsor terminates the study). Maximum treatment duration with pembrolizumab is 24 months.

In case a patient voluntarily discontinues from study treatment, the Investigator must make every effort to determine the primary reason for the decision and record this information in the eCRF.

If a patient withdraws consent for participation in the study, all data collected up to the point of withdrawal must be maintained in the database and included in subsequent analyses, as appropriate. A patient may withdraw from the interventional portion of the study, but agree to continue follow-up of associated clinical outcome information in which case this information would be collected and maintained in the clinical trial database.

Patients who discontinue treatment without relapse/disease progression will continue to follow the CT scan assessment schedule until disease progression, start of new anti-neoplastic therapy, withdrawal of consent, completion of one year of follow-up, lost to follow-up, or end of study (see Table 11), whichever comes first.

Patients may be withdrawn permanently from the study if any of the following occur:

- Adverse event
- Progressive disease or relapse per RECIST v1.1 or iRECIST (for patients receiving pembrolizumab only)
- Lost to follow-up
- Physician decision
- Pregnancy
- Withdrawal of consent
- Study terminated by Sponsor
- Any protocol deviation for which continuing participation in the study would result in a significant risk to the patient's safety

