9.6.2. Secondary Efficacy Endpoints Analysis

Secondary efficacy endpoints will include DOR, disease control rate (DCR), PFS, and OS:

- **Duration of response** (DOR): defined as the interval from date of first observed CR or PR to the date of documented disease progression or death due to any cause, whichever occurs first. All patients who have not progressed will be censored at the last non-missing tumor assessment. Estimates of median DOR with 95% CI will be determined by dosing regimen using Kaplan-Meier methods.
- **Disease control rate** (DCR): defined as the percentage of patients having a CR, PR, or stable disease at any time during treatment, as assessed by the Investigator using RECIST v1.1. DCR will be summarized by dosing regimen with 95% CI obtained by Clopper-Pearson Exact methods.
- Progression-free survival (PFS): defined as the interval from the start of study drug treatment to the date of first documented disease progression or death from any cause, whichever occurs first. Responding patients and patients who are lost to follow-up will be censored at their last tumor assessment date. Estimates of median PFS with 95% CI will be determined by dosing regimen using Kaplan-Meier methods. The 95% CI around the PFS and OS rates at 12 months (56 weeks) will also be presented.
- Overall survival (OS): defined as the interval from the start of study drug treatment to date of death for any reason. Surviving patients and patients who are lost to follow-up will be censored at their contact date. Estimates of median OS with 95% CI will be determined by dosing regimen using Kaplan-Meier methods.

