4.5.5.2 Handling of Dropouts or Missing Data

Objective response rate and disease control rate are based on those patients with available data (baseline and post-baseline response assessment). Non-evaluable patients are considered non-responders and will be included in the denominator. The analysis of PFS and DOR will be right-censored according to the conventions described in [Table 2](#). These conventions are based on the FDA Guidance for Industry *Clinical Trial Endpoints for the Approval of Cancer Drugs and Biologics* ([2018](#)) and *Clinical*

Trial Endpoints for the Approval of Non-Small Cell Lung Cancer Drugs and Biologics (2015).

Table 2 Conventions for Censoring for DOR and PFS

Situation	Date of Progression or Censoring	Outcome
No baseline tumor assessments	Randomization (if applicable), or enrollment	Censored
New anti-cancer treatment started before documentation of PD or death	Date of last disease assessment without documentation of PD before start of new treatment	Censored
Death or progressive disease (PD) immediately after more than one consecutively missed disease assessment visit	Date of last disease assessment visit without documentation of PD that is before the first missed visit	Censored
Alive and without PD documentation	Date of last disease assessment	Censored
Treatment discontinuation for undocumented progression, toxicity, or other reason	Date of last disease assessment without documentation of PD	Censored
Death or PD between planned disease assessments	Date of death or first disease assessment showing PD, whichever occurs first	Not Censored
Death or PD after more than one missed visit	Date of last disease assessment without documentation of PD	Censored

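### SAP 3.4.1.2 lets new therapy, consent withdrawal and loss to follow-up end PFS, against the protocol and SAP Table 2; Table 2 also lacks an order of precedence, and the 12-month landmark is labelled 56 weeks

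*SAP*

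**What the plan says.** **PFS definition.** SAP 3.4.1.2 starts PFS when study drug starts and gives its end point as "first documented disease progression, initiation of new antineoplastic therapy, withdrawal of consent, loss to follow-up, or death due to any cause, whichever occurs first". The same bullet adds: "Dates of progression and censoring will be determined as described in" Section 4.5.5.2, which holds Table 2. Protocol 9.6.2 ends PFS at "the date of first documented disease progression or death from any cause, whichever occurs first", and states: "Responding patients and patients who are lost to follow-up will be censored at their last tumor assessment date". The protocol synopsis and protocol Table 3 also use progression or death only.

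**Censoring rules.** SAP Table 2 covers both DOR and PFS. The row "New anti-cancer treatment started before documentation of PD or death" is censored at the last PD-free assessment before the new treatment. The row "Treatment discontinuation for undocumented progression, toxicity, or other reason" is censored at the last PD-free assessment. The row "Death or PD between planned disease assessments" is not censored. No row names consent withdrawal or loss to follow-up; these fall under the general row for patients alive with no documented PD. No order of precedence is given.

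**Follow-up after stopping treatment.** Protocol 7.3.3 says: "Patients who discontinue treatment without relapse/disease progression will continue to follow the CT scan assessment schedule until disease progression", new therapy, one year of follow-up or another listed stop. SAP 3.1 puts these scans at 12-week intervals.

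**Landmark.** SAP 4.5.4 and protocol 9.6.2 both equate the 12-month PFS and OS landmark with 56 weeks. SAP 4.1.5 converts days to months by dividing by 365.25/12.

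**Declared changes.** SAP 4.8 presents two items as the only changes from the protocol: ORR added as a primary efficacy endpoint for Phase 1b, and no summaries by disease subtype. Neither concerns PFS.

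**The concern.** The SAP holds two rules for the same endpoint. One lists three non-progression exits as ends of the interval, on the same footing as PD and death. The other censors them, at an earlier date. If the definition is programmed as it stands, patients who leave without progressing count as events and PFS comes out too short.

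Table 2 has a second ambiguity. A patient who stops for toxicity and later shows PD on a follow-up scan fits both a censoring row and an event row. If the discontinuation row is applied, a real event is dropped. Because Table 2 also governs DOR, this reaches two endpoints.

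The third fault is numerical: a rate labelled 12 months may be read off the curve almost four weeks late.

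Phase 2 was not run, but SAP 4.5.4 has no phase limit, so PFS and OS will be reported for Phase 1b.

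**Working it through.** **1. The PFS rules side by side**

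| Exit | SAP 3.4.1.2 wording | SAP Table 2 | Protocol 9.6.2 |
|---|---|---|---|
| PD or death | Ends PFS | Event, subject to the new-therapy and missed-visit rows | Event |
| New therapy | Ends PFS on that date | Censored at last PD-free scan before it | Not an event |
| Loss to follow-up | Ends PFS on that date | Not named; general row censors at last assessment | Censored at last tumor assessment |
| Consent withdrawal | Ends PFS on that date | Not named; same general row | Not an event |

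The DOR bullet just above carries the same pointer to 4.5.5.2 yet is defined by progression or death only. The pointer therefore does not account for the extra terms in the PFS bullet.

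**2. Two patients on the planned scans.** SAP 3.1 gives scans at Weeks 8, 14, 20 and 26, then 38, 50, 62.

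- Patient 1 is stable at Week 14 and starts new therapy at Week 16. The 3.4.1.2 wording ends PFS at Week 16, as an event if read literally. Table 2 censors at Week 14.
- Patient 2 is stable at Week 14, stops for toxicity at Week 16, has no new therapy, and shows PD on the 12-weekly follow-up scan at Week 26 (14 + 12). The discontinuation row censors at Week 14. The not-censored row gives an event at Week 26.

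**3. Size if the literal wording is used.** Assume constant hazards and let q be the share of intervals ended first by one of the three added exits. The composite hazard is the PD-or-death hazard divided by (1 − q), so composite median = (1 − q) × M. The documents give no value for q. For illustration take M = 6.5 months, which protocol 1.2.1 reports for a pembrolizumab study and not for this regimen. The 12-month rate is 2^(−12/median).

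| q (assumed) | Median, months | 12-month PFS |
|---|---|---|
| 0 | 6.50 | 27.8% |
| 10% | 5.85 | 24.1% |
| 20% | 5.20 | 20.2% |
| 30% | 4.55 | 16.1% |

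**4. The landmark.** One month is 365.25/12 = 30.4375 days.

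- 56 weeks = 56 × 7 = 392 days; 392/30.4375 = 12.88 months.
- 12 months = 365.25 days; 365.25/7 = 52.18 weeks.
- Gap: 392 − 365.25 = 26.75 days, or 0.88 months.

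The plan's equation of 12 months with 56 weeks cannot be reproduced. A 365-day year gives 52.14 weeks, twelve 30-day months 51.43, twelve 28-day months 48 and thirteen 28-day periods 52. The documents' own 26 weeks for 6 months does reproduce (182/30.4375 = 5.98) and implies 52 weeks for 12 months. Week 56 is not a planned scan.

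**5. Effect on OS.** With S(t) = 2^(−t/median) and assumed medians:

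| OS median, months | S(12) | S(12.88) | Fall, points |
|---|---|---|---|
| 12 | 50.0% | 47.5% | 2.5 |
| 18 | 63.0% | 60.9% | 2.1 |
| 24 | 70.7% | 68.9% | 1.8 |

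**6. Effect on PFS.** With a ±1-week window the scans around the landmark fall no later than Week 51 and no earlier than Week 61. No scheduled scan lies between Weeks 52.18 and 56, so scan-detected PD contributes nothing and only deaths move the curve. If deaths are a share d of the hazard, the fall is about S(50 weeks) × d × (ln 2/median) × 0.88, with 50 weeks = 350/30.4375 = 11.50 months.

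- Median 6.5 months, d = 10%: 0.293 × 0.10 × 0.1066 × 0.88 ≈ 0.0027, or 0.27 points; d = 20% doubles this to about 0.55.
- Median 12 months, d = 10%: 0.515 × 0.10 × 0.0578 × 0.88 ≈ 0.0026, or 0.26 points; d = 20% gives about 0.5.

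A simulation with 4,000,000 draws gave 0.27 and 0.55 points at a 6.5-month median, 0.26 and 0.51 at 12 months, and 0 when d = 0. Unscheduled or end-of-treatment scans in the gap are ignored.

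**The case against.** The strongest defence is that the PFS bullet sends dates and censoring to Section 4.5.5.2, and Table 2 is directive. A programmer who follows it censors all three exits. For loss to follow-up, the general row gives the same date as the protocol. On that reading no event status changes and the undeclared change is loose wording. This stands in large part: nothing shows the literal reading will be used, and the 10% to 30% fall only returns the assumed share. It does not remove the contradiction, because a definition and its censoring table should not disagree.

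On Table 2, the discontinuation row may be a deliberate convention, since 4.5.5.2 says the rules rest on FDA guidance that was not available for this check. Limiting the row to patients with no later PD or death also makes it give the same result as the general row for patients alive without PD. That is fair. But the protocol defines PFS by PD or death from any cause and keeps scanning after treatment stops. If censoring at discontinuation is intended, the SAP should say so and declare it. The lack of precedence is also not confined to this row; this is where it matters most.

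On size, the 56-week label is inherited from the protocol, so it is not a protocol–SAP difference. In cohorts of 3 to 6 one death moves a Kaplan–Meier estimate by about 33 to 17 points (1/3 to 1/6), and over 27 to 60 pooled patients by 3.7 to 1.7 points. The landmark shift is therefore roughly one patient or less. SAP 4.8 also moved long-term follow-up patients to End of Study, so few may resemble Patient 2. All of this limits the consequence, not the error.

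**Conclusion.** The point holds and should be fixed.

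- **Definition.** The PFS definition in SAP 3.4.1.2 contradicts the protocol and SAP Table 2 and is not declared in 4.8. The damage is conditional on literal programming. Its size depends on the unknown share of non-progression exits and, with constant hazards, equals that share as a proportional fall in the median.
- **Precedence.** Table 2 supports two outcomes for a patient with PD or death documented after stopping treatment. It probably affects few patients, but in cohorts of 3 to 6 a single reclassified patient can visibly change the curve.
- **Landmark.** 56 weeks is 12.88 months. The cost is 1.8 to 2.5 points on OS for assumed exponential medians of 24 to 12 months. For PFS it is 0 to about 0.5 points, assuming scheduled scans only and deaths as at most 20% of events.

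PFS and OS are secondary and descriptive, and only Phase 1b is analysed, so no test or decision rule depends on them. Confidence is high that the texts conflict; the bias in the reported results cannot be determined from the documents.

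**What to change.** Change the SAP only:

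1. In 3.4.1.2, define PFS as time to first documented PD or death from any cause. Add two rows to Table 2 that censor consent withdrawal and loss to follow-up at the last disease assessment.
2. Keep the treatment-discontinuation row but limit it to patients with no later documented PD or death. State that the new-therapy and missed-visit rules still apply.
3. In 4.5.4, state the landmark as 12 months (365.25 days, about 52 weeks). Add a line in 4.8 noting that this corrects the protocol's 56-week label.

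The cost is one definition, two added rows, one limited row, one label and one line in 4.8. No new data and no protocol amendment are needed. If the sponsor does want the wider PFS definition, or censoring at treatment discontinuation whatever follows, it should say so and declare it in 4.8.

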3.4.2 Safety Variables

3.4.2.1 Adverse Events

An AE is any untoward medical event that occurs to a patient following the start of administration of the study treatment, whether or not the event is considered study drug related. Any worsening (i.e., any clinically significant adverse change in the frequency or intensity of a pre-existing condition) should be considered an AE.

For all patients (excluding those in Phase 2 receiving nanatinostat, valganciclovir, and pembrolizumab), AEs will be recorded from the signing of the informed consent form (ICF) up to and including 30 days (90 days for SAEs) after the last dose of study treatment or until the start of subsequent anticancer therapy, whichever occurs first. For patients in Phase 2 who receive nanatinostat, valganciclovir, and pembrolizumab, AEs will be recorded from the signing of the ICF up to and including 90 days after the last dose of study treatment or until a new anticancer treatment is started, whichever is first.

3.4.2.2 Laboratory Parameters

Laboratory tests will be collected and analyzed in central or local laboratories. Assessments include hematology, coagulation, serum chemistry, urinalysis, viral levels, and pregnancy testing (only for females of childbearing potential). Specific parameters include the following:

- Hematology: Hemoglobin, platelets, and white blood cell count with differential (absolute neutrophils, absolute monocytes, absolute eosinophils, absolute lymphocytes, absolute basophils);
- Coagulation: prothrombin time or international normalized ratio, and activated partial thromboplastin time;
- Serum Chemistry: aspartate aminotransferase, alanine aminotransferase, albumin, total bilirubin, sodium, potassium, magnesium, total protein, alkaline phosphatase, bicarbonate, blood urea nitrogen, creatinine, glucose (non-fasting), chloride, calcium, phosphate, uric acid, and thyroid function tests (Phase 2 only [thyroid-stimulating hormone, free T3, free T4])
- Urinalysis (Dipstick): pH, specific gravity, glucose, bilirubin, ketones, blood, protein, urobilinogen, nitrite/nitrate, leukocytes/leukocyte esterase; and
- Viral: Hepatitis B virus (HBV) surface antigen, HBV core and surface antibody, HBV DNA polymerase chain reaction (for patients with positive HBV core antibody or surface antigen), Hepatitis C virus (HCV) antibody (for patients with positive HCV antibody), and EBV DNA, cytomegalovirus, and human immunodeficiency virus levels (HIV), for HIV⁺ patients only.

3.4.2.3 Other Safety Variables

All 12-lead ECGs will be conducted in triplicate. Triplicate 12-lead ECGs will be performed separated by approximately 1 minute at screening, on Cycle 1 Day 1 (Phase 1b, all dose levels, and Phase 2), Cycle 2 Day 1 (Phase 1b dose levels 8 through 13 and Phase 2 only) and at the EOT visit. Prior to each ECG, the patient will lie in a supine position in a calm environment for at least 5 minutes.

When performed in concert with serial PK collection on Cycle 1 Day 1 (for Phase 1b dose levels 1 through 7), two ECGs will be performed pre-dose (within 1 hour of dose, separated by at least 15 minutes). Post-dose ECGs will be performed prior to and as close as possible to each PK sample collection at approximately maximum plasma concentration (1 and 2 hours), 4 hours, and 6 hours.

When performed in concert with serial PK collection on Cycle 1 Day 1 (for Phase 1b dose levels 8 through 13 and Phase 2), two ECGs will be performed pre-dose (within 1 hour of dose, separated by at least 15 minutes) and one set of triplicate 12-lead ECGs will be performed on Cycle 1 Day 1 at 2-hours post-dose. When performed in concert with serial PK collection on Cycle 2 Day 1 for these patients, two ECGs will be performed pre-dose (within 1 hour of dose, separated by at least 15 minutes). Post-dose ECGs will be performed prior to and as close as possible to each PK sample collection at approximately maximum plasma concentration (1 and 2 hours), 3 hours, 4 hours, 5 hours, and 6 hours.

At screening and at the EOT visit, the ECG may be performed at any time during the clinic visit. ECGs may also be performed when clinically indicated, irrespective of the time of study drug dosing.

Vital signs (temperature, blood pressure, and heart rate) will be collected at the screening visit (Day -28 to Day -1), on Day 1 of each cycle, and at the EOT visit. On visit days requiring serial PK collection, vital signs will be collected just prior to the first dose of valganciclovir and nanatinostat, and in concert and just prior to PK blood draws. On other indicated visit days, vital signs will be collected once (prior to dosing of study treatment if administered in clinic).

A physical examination will be conducted at the screening visit, at the beginning of each cycle, at the EOT visit, and at any additional times deemed necessary by the Investigator. Height and weight will be measured at the screening visit and weight will be subsequently measured on Day 1 of each cycle and at the EOT visit.

The ECOG performance status will be assessed at the screening visit, on Cycle 1 Day 1, and at the EOT visit.

